#### **ABBREVIATIONS**

AAV adeno-associated virus

ACTH adrenocorticotropic hormone AE adverse event/experience

AFP α-fetoprotein

ALT alanine aminotransferase (SGPT)

ANSI American National Standards Institute

AQL acceptable quality level

AST aspartate aminotransferase (SGOT)
ATC Anatomical, Therapeutic, and Chemical
BSID-III Bayley Scales of Infant Development

CDA clinical data associate

eCRF electronic case report form

CTCAE Common Terminology Criteria for Adverse Events

CSF cerebrospinal fluid
DS dermatan sulfate
ECG electrocardiogram
ECHO echocardiogram
EOS End of Study Visit

ERT enzyme replacement therapy

FVC forced vital capacity
GAG glycosaminoglycan

hIDS human iduronate-2-sulfatase

HS heparan sulfate

IDS iduronate-2-sulfatase JROM joint range of motion LDH lactate dehydrogenase

MedDRA Medical Dictionary for Regulatory Activities

MPS II Mucopolysaccharidosis II
MRI magnetic resonance imaging
PFT pulmonary function test

PT Preferred Term QC quality control

rAAV recombinant adeno-associated virus

RDC remote data capture
SAE serious adverse event
SAP statistical analysis plan

SMC Safety Monitoring Committee

SOC System Organ Class

TEAE treatment emergent adverse event

CONFIDENTIAL Page 6 of 28

VABS-II Vineland Adaptive Behavior Scales

WASI-II Wechsler Abbreviated Scale of Intelligence, Second Edition; Shapiro et al. 2015

WPPSI-IV Wechsler Preschool and Primary Scale of Intelligence

WHO World Health Organization

ZFN zinc finger nuclease 6MWT 6-minute walk test

CONFIDENTIAL Page 7 of 28

#### 1. INTRODUCTION

This document details the Statistical Analysis Plan (SAP) for Protocol SB-913-1602, A Phase 1/2, Multicenter, Open-label, Single-dose, Dose-ranging Study to Assess the Safety and Tolerability of SB-913, a rAAV2/6-based Gene Transfer in Subjects with Mucopolysaccharidosis II (MPS II). The SAP summarizes key aspects of the study to provide context for statistical methods and presents details of the planned statistical methods addressing the study aims.

#### 2. OBJECTIVES AND ENDPOINTS

#### 2.1 Objectives

# 2.1.1 Primary Objective

To evaluate the safety and tolerability of SB-913.

# 2.1.2 Secondary Objectives

- To evaluate change from baseline over time in the following assessments:
  - o Iduronate-2-sulfatase (IDS) activity in blood
  - o Glycosaminoglycan (GAG) testing in urine
- Frequency of enzyme replacement therapy (ERT) administration
- Adeno-associated virus (AAV) 2/6 clearance

#### 2.1.3 Exploratory Objectives

To evaluate change from baseline over time in the following assessments:

- Gene modification at the albumin locus in the liver
- Imaging, functional, and neurocognitive testing related to MPS II
- Immune response to AAV2/6, and zinc finger nucleases (ZFNs), and IDS

### 2.2 Endpoints

#### 2.2.1 Primary Endpoint

The primary endpoint of this study is the incidence of treatment-emergent adverse events (TEAEs) including serious adverse events (SAEs).

Additional safety evaluations will include:

- Routine hematology, chemistry, and liver function laboratory tests, vital signs, physical exam, electrocardiogram (ECG), echocardiogram (ECHO), and concomitant medications.
- Cranial nerve exam and muscle strength testing.
- Serial  $\alpha$ -fetoprotein (AFP) testing and magnetic resonance imaging (MRI) of liver to evaluate for liver mass.

CONFIDENTIAL Page 8 of 28

Safety assessment will be performed on all subjects. TEAEs will be summarized overall and by treatment cohort. For each subject, the maximum reported severity of each adverse event will be used in the summaries by severity grade. In addition, all SAEs and AEs related to study treatment will be summarized.

# 2.2.2 Secondary Endpoints

The following are secondary endpoints for this study:

- Change from Baseline in:
  - o IDS activity measured in blood.
  - o Total GAG, DS GAG, and HS GAG levels (expressed as ratio to creatinine) measured in urine.
- Monthly and annualized frequency and dose of idursulfase (or equivalent ERT).
- AAV2/6 clearance measured by vector genomes in plasma, saliva, urine, stool, and semen by PCR.

#### 2.2.3 Exploratory Endpoints

Change from baseline over time in the following assessments:

- Percentage and durability of gene modification at the albumin locus in liver tissue obtained at biopsy.
- Forced vital capacity (FVC) measured by pulmonary function tests (PFTs).
- Distance walked measured by six-minute walk test (6MWT).
- Joint range of motion (JROM).
- MRI of liver to evaluate liver and spleen volume.
- MRI of brain and cervical spine to evaluate clinical soft tissue and/or bone.
- Neurocognitive abilities by WASI-II (Wechsler Abbreviated Scale of Intelligence, Second Edition; Shapiro et al. 2015), WPPSI-IV (Wechsler Preschool and Primary Scale of Intelligence), or BSID-III (Bayley Scales of Infant Development), and by VABS-II (Vineland Adaptive Behavior Scales).
- Histopathological exam of liver tissue.
- Immune response to AAV 2/6, ZFNs, and IDS measured in serum.

#### 3. INVESTIGATIONAL PLAN

#### 3.1 Study Design

This is a Phase 1/2, multicenter, open-label, single-dose, dose-ranging study with sequentially enrolled age cohorts: age  $\geq$ 18 (adult cohorts 1 through 4), age 12-17 (pediatric cohorts 5 and 6), and age 5-11 (pediatric cohorts 7 and 8).

Subjects who satisfy all eligibility criteria will be enrolled into one of the following treatment

CONFIDENTIAL Page 9 of 28

cohorts:

Cohort #	Age Range (years)	Total Dose (vg/kg)	# Subjects
1	≥18	5.00E+12	2
2	≥18	1.00E+13	2
3	≥18	5.00E+13	2
4	≥18	1.20E+14	2
5	12-17	5.00E+13	2
6	12-17	TBD	2
7	5-11	TBD	2
8	5-11	TBD	2

Two subjects will be enrolled in each cohort, and will be dosed at least 4 weeks apart. SMC (Safety Monitoring Committee) review occurs after at least 4 weeks of safety data is available from 2 subjects in each cohort. The pediatric cohorts will be enrolled only after review of cumulative adult safety data by the SMC. The starting dose for pediatric cohorts 6 through 8 will be decided based on SMC review of study data, and must meet pre-defined safety criteria. Approximately 2 additional subjects may be added to any age cohort after SMC review of study data if safety criteria are met, with up to a total of 32 subjects in the study.

For subject inclusion and exclusion criteria, please refer to study protocol SB-913-1602. Subjects that do not complete at least 12 months of the study may be replaced with other subjects. The duration of the study participation will be approximately 39 months for each subject, divided into approximately 3 months for Screening followed by 36 months for treatment and study follow-up. Upon completion of the study, subjects will be asked to participate in a separate Long-term Follow-up Study to monitor the long-term safety of SB-913.

A detailed schedule of events for the study can be found in Appendix A.

#### 3.2 Treatment

#### 3.2.1 Randomization Scheme and Treatment Arm Assignment

This is an open-label study, there is no randomization scheme.

The doses of SB-913 selected for evaluation in this study are:

Cohort	ZFN 1 (SB-47171) (vg/kg)	ZFN 2 (SB-47898) (vg/kg)	hIDS Donor (SB-IDS) (vg/kg)	Total rAAV (vg/kg)
1	5.00E+11	5.00E+11	4.00E+12	5.00E+12
2	1.00E+12	1.00E+12	8.00E+12	1.00E+13
3	3 5.00E+12		4.00E+13	5.00E+13

CONFIDENTIAL Page 10 of 28

4	1.20E+12	1.20E+13	9.60E+13	1.20E+14
5	5.00E+12	5.00E+12	4.00E+13	5.00E+13
6	TBD	TBD	TBD	TBD
7	TBD	TBD	TBD	TBD
8	TBD	TBD	TBD	TBD

# 3.2.2 Blinding

This is an open-label study, there is no blinding.

# 3.2.3 Dosing Schedule

The 3 components of SB-913 (ZFN1, ZFN2, and human iduronate-2-sulfatase (hIDS) Donor) will each be added to 200 mL of diluent and adjusted to 0.25% human serum albumin. Total infusion volumes will depend on subject's cohort assignment and body weight (kg). IV infusions will be administered while the subject is in the hospital or acute care facility. The subject will remain in the hospital or acute care facility for at least 24 hours after SB-913 infusion for observation, and will be discharged when all AEs and vital signs (temperature, heart rate, respiratory rate, and blood pressure) are stable. After being discharged from the hospital or acute care facility, subject will be evaluated at regular clinic visits throughout the study.

# 3.2.4 Subject Compliance

Subjects who prematurely discontinue the study prior to the 12 months of study follow-up (i.e., subjects who were enrolled but not dosed, lost to follow-up, or discontinued prematurely for another reason) may be replaced at the discretion of Sangamo.

#### 4. GENERAL CONSIDERATIONS FOR DATA ANALYSIS

As a first-in-human and first-in-subject proof-of-concept trial there are no statistical hypotheses regarding treatment effects. Rather, displays and comparisons of study results – regarding dose-related safety profiles among the dose cohorts – will primarily utilize descriptive statistics, as noted below.

Unless otherwise specified, continuous variables will be summarized by presenting the number of non-missing observations, mean, standard deviation, median, minimum, and maximum. Categorical variables will be summarized by presenting the number of subjects and percentage for each category.

Summary results will be provided for each dose cohort. All tabulations will be based on pooled data across centers.

Analyses will be performed using SAS for Windows statistical software, version 9.2 or higher (SAS, Cary, NC), except where other software may be deemed more appropriate.

CTI Clinical Trial and Consulting Services (Covington, KY) will perform all safety, primary, secondary, and exploratory endpoint statistical analyses.

Subject data will be listed, sorted by dose cohort and subject number.

CONFIDENTIAL Page 11 of 28

#### 4.1 Data Quality Assurance

Sangamo Therapeutics, Inc., or its designated representative, will conduct a pre-study visit for each study site to verify the qualifications of the investigator, inspect study site facilities, become familiarized with site staff assigned to the study, and inform the investigator of responsibilities and procedures for ensuring correct study documentation.

A study coordinator at the investigative site will enter subject data into MediData RAVE EDC by completing electronic case report forms (eCRFs). All information recorded in the eCRFs for this study must be consistent with the investigator's source documentation for the study participants. The investigative site will make available source documents to CTI personnel monitoring the study. The study monitor will verify consent of all subjects to participate in the study and will perform 100% source document verification of the eCRF data.

A CTI Clinical Data Associate (CDA) will review the data for discrepancies via programmed electronic consistency checks, data listings, or manually. Any discrepancies discovered via the data review process will be issued as queries in the EDC system to the investigative site for resolution. Once all the source verification is complete, all queries are resolved, and the database has been updated appropriately, the database will be locked and made available to CTI Biostatistics for analysis.

Data may be pulled by CTI Biostatistics for SMC analysis at a time when source verification and query resolution is ongoing.

All SAS programs used to create analysis datasets and output will be validated by ensuring that the ".log" files are void of all errors, warnings and notes indicative of problems. Additionally, each program will be checked to ensure that it performs according to the program specification. All programs are developed and validated by separate members of the CTI Biostatistics Department.

When performing a quality control (QC) review of listings and tables output from SAS, it is not always possible to perform a 100% QC review of all fields. If a 100% QC review is not to be performed, the sample size of fields to undergo QC review may be determined by utilizing American National Standards Institute (ANSI) sampling procedures. Sampling procedures are conducted using "normal" inspection criteria (Inspection Level II, Single, and Normal) and an Acceptable Quality Level (AQL) of 0.010%. The following shows the sampling criteria:

Single Normal sampling procedure for Acceptable Quality Level (AQL) 0.010%

Number of Fields	Sample Size	Accept/Reject Criteria
2-8	2	0/1
9-15	3	0/1
16-25	5	0/1
26-50	8	0/1
51-90	13	0/1
91-150	20	0/1
151-280	32	0/1
281-500	50	0/1

CONFIDENTIAL Page 12 of 28

Number of Fields	Sample Size	Accept/Reject Criteria
501-1,200	80	0/1
1,201-3,200	125	0/1
3,201-10,000	200	0/1
10,001-35,000	315	0/1
35,001-150,000	500	0/1
150,001-500,000	800	0/1
500,001-up	1,250	0/1

# 4.2 Analysis Sets

All subjects enrolled in this study who receive any portion of the SB-913 infusion will be included in the Safety Analysis Set . All analyses (i.e., safety, primary, secondary, and exploratory) will be performed using the Safety Analysis Set .

#### 4.3 Assessment Windows

For the purpose of listing and summarizing data, the time-in-study for each subject observation will be defined using study days, weeks and months. Such days will be measured relative to Day 0, the day on which SB-913 is infused. Because protocol-specified visits (e.g., Week 16) will not necessarily occur on the same study day for all subjects, study visits will be defined through the use of windows. Study visits will have windows as per the following schema:

Data will be summarized based on the CRF (Study Visit) in which it was collected.

Baseline will be defined as the last pretreatment value during the screening period except for the GAG/IDS values. For the GAG/IDS test, baseline will be calculated using the mean of all prior dosing values. If more than one assessment exists within a single visit window, the value closest to the protocol study visit will be used for summary and analysis purposes. Data from all assessments will be listed.

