3.4 Study Duration

The duration of study participation will be approximately 39 months for each subject (see Figure 9), divided into approximately 3 months for Screening followed by 36 months for treatment and study follow-up.

Figure 9. Schema of Study Visits.

Upon completion of the study, subjects will be asked to participate in a separate Long-term Follow-Up (LTFU) Study to monitor the long-term safety of SB-913. To alleviate study burden, study subjects may participate in the LTFU Study after at least 12 months of follow-up in this study. Study participants who wish to enroll in the LTFU Study with less than 12 months of follow-up in this primary study may be considered on a case-by-case basis at the judgement of the Principal Investigator and after consultation with the Sponsor.

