- Immunogenicity assays (at Weeks 12, 24, 36, and 48 only).
- Prednisone or equivalent corticosteroid administration (through Week 20 only).

6.9 Months 15, 18, 21, 24, 27, 30, 33, and 36/End of Study (+/-1 month)

Subjects will be evaluated every 3 months in Years 2 and 3 after SB-913 infusion.

An End of Study (EOS) visit will be conducted at Month 36.

At the EOS visit, subjects will be asked to participate in the LTFU Study. Study subjects may participate in the LTFU Study after 12 months of follow-up in this study, in which case an EOS visit may be conducted anytime after Week 52 but before the next scheduled study visit.. Study participants who wish to enroll in the LTFU Study with less than 12 months of follow-up in this primary study may be considered on a case-by-case basis at the judgement of the Principal Investigator and after consultation with the Sponsor. In these cases, EOS visit may be conducted anytime when transition to the LTFU study is imminent. Informed consent will be obtained prior to participating in the LTFU Study.

The following assessments and procedures will be performed unless otherwise stipulated:

- Review and record concomitant medications.
- Physical examination.
- Vital signs.
- Assessment of AEs.
- ERT administration log.
- JROM (at Months 18, 24, 30, and 36/EOS only).
- Neurologic cranial nerve exam and muscle strength testing of the upper extremities (at Months 18, 24, 30, and 36/EOS only).
- 12-lead ECG (at Months 18, 24, 30, and 36/EOS only).
- ECHO (at Months 24 and 36/EOS only).
- Clinical laboratory tests.
- Liver panel.
- GAG testing in urine.

- IDS / GAG testing in blood.
- Circulating AFP level (at Months 18, 24, 30, and 36/EOS only).
- PFTs (at Months 18, 24, 30, and 36/EOS only).
- 6MWT (at Months 18, 24, 30, and 36/EOS only).
- Neurocognitive abilities tests by WASI-II, WPPSI-IV, or BSID-III, and by VABS-II (at Months 18, 24, 30, and 36/EOS only).
- MRI of liver (at Months 18, 24, 30 and 36/EOS only).
- MRI of brain and cervical spine (at Months 24 and 36/EOS only).
- Immunogenicity assays (at Months 18 and 24 only).

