#### 4.4 Study Days

For the purpose of the analysis, study day will be calculated relative to first administration of the study drug. Specifically:

If visit date is prior to dosing:

Study day = date of visit - first dose date

If visit date is on or after dosing:

Study day = date of visit – first dose date + 1.

Statistical analyses will be performed using study day as defined above.

CONFIDENTIAL Page 13 of 28

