#### 6.2 Secondary Endpoints and Analyses

Secondary endpoints will be summarized by presenting descriptive statistics of actual values and changes from baseline at each visit, where applicable. The secondary endpoints consist of the changes from baseline over time in the following assessments:

- IDS activity measured in plasma
- Assessments will be conducted at Screening, Baseline, Weeks 2, 4, 6, 8, 12, 16, 20, 24, 36, 48, Months 15, 18, 21, 24, 27, 30, 33, 36/End of Study (EOS), and at any Early Termination Visit. Total GAG, dermatan sulfate (DS) GAG, and heparin sulfate (HS) GAG levels measured in urine

At each sampling time point, the actual value and the change from baseline for IDS activity and urine GAG levels will be summarized using descriptive statistics and plotted over time by treatment cohort.

For subjects who undergo ERT withdrawal, changes from pre- to post- ERT withdrawal in the frequency and dose of ERT infusions will be evaluated and summarized using monthly, quarterly, and annualized total dose and number of infusions. Duration of ERT withdrawal may also be analyzed. The ERT withdrawal period is defined as the date recorded on the ERT Withdrawal Trigger CRF form to the first date after ERT withdrawal recorded on the ERT administration.

• AAV2/6 clearance measured by vector genomes in plasma, saliva, urine, stool, and semen by PCR

AAV2/6 clearance measured by vector genomes in the different samples will be plotted over time by treatment cohort.

CONFIDENTIAL Page 15 of 28

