			Hospital or		Day								W	Veek							П			M	font	1			
PROCEDURE	Screening (p)	Baseline	Acute Faci	Care	7	2	4	6	8 1	2 1	6 20	2	24 2	28±	32*	36	40*	44*	48	52*	15	18	21	24	27	30	33	36 EOS	EIV
	(win 3 months of Baseline)	(win 21 days prior to SB-913 infusion)	Day 0	Day 1	(+/-1 day)	(+	+/-2 6	lays)						(	+/-1 w	eek)						(+/-1 month)							
VABS-II	X	X										3	X						X			Х		X		X		X	X
Neurocognitive Abilities Assessment	x																												
Neurocognitive Abilities Testing (j)		х										3	x						x			x		x		x		x	x
MRI of Liver	X						П					3	X						Х			х		Х		Х		X	X
MRI of Brain and Cervical Spine (k)		x																	x					x				X	x
ACTH Stimulation (Cosyntropin) Test (1)		X (prior to prednisone)									х																		
Liver Biopsy (m)		X					П					3	X						Х										
Lumbar Puncture (m)		х										3	x						x										
Immunogenicity Assays (n)		х					x		Z	2		3	x			x			x			x		x					
Prednisone (or equivalent corticosteroid) Administration (o)		х	х				X		•		•																		
SB-913 Infusion			X				П	П		Т		T																	

CONFIDENTIAL Page 24 of 28

\* Week 28, 32, 40, 44, and 52 study visits have assessments that do not require evaluation at the clinical site, and therefore may be conducted at home if the subject is remote. Blood and urine samples at these visits may be collected by a qualified home health nurse. Assessments for AEs, concomitant medications and ERT administration log may be conducted remotely over the phone by study staff.

- § Study subjects may participate in the LTFU Study after 12 months of follow-up in this study, in which case an EOS visit may be conducted any time after Week 52 but before the next scheduled study visit. Study participants who wish to enroll in the LTFU Study with less than 12 months of follow-up in this primary study may be considered on a case-by-case basis at the judgement of the Principal Investigator and after consultation with the Sponsor. In these cases, the EOS visit may be conducted at any time on this study.
- a. Vital signs (height, weight, systolic/diastolic blood pressure, heart rate, respiratory rate, and temperature; for frequency, refer to the Study Reference Manual).
- b. As permitted by subject's capacity.

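### Early EOS values may be summarised in the Month 36/EOS row, and no table reports follow-up time beside the crude TEAE figures by dose cohort

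*SAP*

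**What the plan says.** **Early exit is a planned route.** Follow-up after dosing is 36 months, but under Protocol 3.4 "study subjects may participate in the LTFU Study after at least 12 months of follow-up in this study". In that case, says Protocol 6.9, "an EOS visit may be conducted anytime after Week 52 but before the next scheduled study visit". Subjects with less than 12 months of follow-up may also move, case by case. For them the footnote to SAP Appendix A says: "In these cases, the EOS visit may be conducted at any time on this study".

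**One EOS label.** SAP 6.2 lists the late visits for IDS activity as "Months 15, 18, 21, 24, 27, 30, 33, 36/End of Study (EOS"), with the Early Termination Visit named separately. SAP 6.3 and 7.3 to 7.9 use the same combined label where they list late visits.

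**How values reach a row.** SAP 4.3 says that "Data will be summarized based on the CRF (Study Visit) in which it was collected". The same section also says that "study visits will be defined through the use of windows", and SAP 4.4 adds: "Statistical analyses will be performed using study day as defined above". Under SAP 4, "continuous variables will be summarized by presenting the number of non-missing observations, mean, standard deviation, median, minimum, and maximum".

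**TEAEs.** SAP 7.2.1 counts events from infusion to the last study visit. SAP 7.2.5 gives, overall and by dose cohort, the number of subjects with an event over the number in the Safety Analysis Set, and the overall table adds total episodes. SAP 7.1 covers dose and infusion interruption. SAP 5.1 gives disposition counts. Neither describes a summary of time followed.

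**The concern.** There are two linked questions.

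The first is which row an early EOS value belongs to. The rule is tabulation by CRF visit, and the only EOS visit named is Month 36/EOS. The natural reading therefore puts an assessment made soon after Week 52 beside true three-year assessments. That row carries IDS activity, AFP, liver and spleen volume, FVC and 6MWT, where a reader would take the values as evidence of durability or late safety.

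The second is whether TEAE figures can be compared between dose cohorts. SAP 4 names dose-related safety profiles among the cohorts as the object of comparison. A crude percentage or raw episode total compares cohorts fairly only if they were followed for similar times. Subjects who move to LTFU early stay in the denominator while their observation stops. So do dosed subjects who leave before 12 months and are replaced, because SAP 4.2 includes anyone who received any portion of the infusion. If early exit differs between cohorts, part of a difference in TEAE figures can come from length of follow-up, and no planned table lets the reader check this.

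**Working it through.** **Inputs from the documents.** Full follow-up is 36 months (SAP 3.1). Earliest routine roll-over is after Week 52: 52 × 7 / 30.4375 = 11.96, about 12 months. For an exit at that point the next scheduled visit is Month 15. There are 8 cohorts of 2, with approximately 2 more possible in any cohort (SAP 9). The stated maximum reproduces: 8 × (2 + 2) = 32. The documents give no early-exit rate and no TEAE rate, so the exits and rates below are assumptions.

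**Step 1: mean time in the Month 36/EOS row, if early values are pooled and one subject exits.**
- Cohort of 2: (12 + 36)/2 = 24 months, or (15 + 36)/2 = 25.5 months. One of 2 values is early.
- Cohort of 4: (12 + 3 × 36)/4 = 30 months, or (15 + 3 × 36)/4 = 30.75 months. One of 4 values is early.
- In a cohort of 2, n in the quarterly laboratory rows would read 2 at Week 48, 1 from Month 15 to Month 33, and 2 again at 36/EOS.

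**Step 2: expected episodes at the same underlying rate.** The ratio is the observation time of a fully followed cohort over that of a cohort with one exit. In the second rate column each completer contributes 12 + 0.25 × 24 = 18 rate units, and an exit contributes 12 (month 12) or 12 + 0.25 × 3 = 12.75 (month 15).

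| One exit at | Cohort | Constant rate | Rate in years 2-3 a quarter of year 1 |
|---|---|---|---|
| 12 months | 2 | 72/48 = 1.50 | 36/30 = 1.20 |
| 15 months | 2 | 72/51 = 1.41 | 36/30.75 = 1.17 |
| 12 months | 4 | 144/120 = 1.20 | 72/66 = 1.09 |
| 15 months | 4 | 144/123 = 1.17 | 72/66.75 = 1.08 |

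Later exits matter less. At a constant rate, one exit at month 24 gives 72/60 = 1.20 (cohort of 2) or 144/132 = 1.09 (cohort of 4), and one at month 30 in a cohort of 2 gives 72/66 = 1.09. Exits before 12 months would matter more. If all events fall in year 1 and no one exits before 12 months, the ratio is 1.0.

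**Step 3: subject incidence.** Suppose half of one cohort exits at 12 months and none of the other. Let p12 be the 12-month risk. With a constant hazard, p36 = 1 − (1 − p12)^3. With a quarter of the hazard in years 2-3, p36 = 1 − (1 − p12)^1.5. The ratio is p36 / [(p12 + p36)/2].

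| p12 | Constant hazard | Quarter hazard |
|---|---|---|
| 5% | 0.1426/0.0963 = 1.48 | 0.0741/0.0620 = 1.19 |
| 20% | 0.488/0.344 = 1.42 | 0.2845/0.2422 = 1.17 |
| 50% | 0.875/0.6875 = 1.27 | 0.6464/0.5732 = 1.13 |
| 95% | 0.9999/0.9749 = 1.03 | 0.9888/0.9694 = 1.02 |

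**Step 4: comparison with chance.** The largest absolute shift in Step 3 is at p12 = 50% with a constant hazard: 0.875 − 0.6875 = 0.1875. The variance of the difference between the two observed proportions is:
- Cohorts of 4: 0.875 × 0.125/4 + (2 × 0.5 × 0.5 + 2 × 0.875 × 0.125)/16 = 0.0273 + 0.0449 = 0.0723, so SD 0.27.
- Cohorts of 2: 0.875 × 0.125/2 + (0.5 × 0.5 + 0.875 × 0.125)/4 = 0.0547 + 0.0898 = 0.1445, so SD 0.38.

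The shift is smaller than one SD in both cases.

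**The case against.** The strongest defence is that SAP 4.3 does give a rule, tabulation by CRF visit, and that only the eCRF's name for an early EOS visit is unknown. If the eCRF has a separate form, no pooling occurs. This stands, and the first half of the point is conditional on it.

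A reader might go further and infer that the SAP contradicts itself, because 4.3 also speaks of windows, 4.4 of study day, and the schedule attaches ±1 month to the Month 36/EOS column. The documents do not support that. The CRF sentence may itself be the announced schema, or a window table may have been lost when the PDF was read. A study-day variable can coexist with tabulation by visit. The ±1 month is a scheduling tolerance, and the LTFU footnote allows an EOS visit outside it.

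Much is also visible already. Non-missing n is planned for continuous summaries, all assessments are listed, AE listings carry onset and resolution dates, liver-panel figures are by subject, and discontinuations are summarised by cohort. With 2 to 4 subjects a careful reader could reconstruct most of it. That limits the harm, but it leaves the row's label and the missing follow-up summary as they are.

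Finally, the ratios rest on assumed exits and rates, and a Week 52 table is one choice among several. Both objections are fair. Twelve months is the protocol's threshold for discretionary replacement. It should not be read as an evaluability criterion for analysis, since everyone who received any infusion is analysed.

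**Conclusion.** The point holds as a minor one. On the natural reading of SAP 4.3, and unless the eCRF separates them, early EOS values enter the Month 36/EOS row. Crude TEAE percentages and episode totals by dose cohort are planned without any table of follow-up time, although that time can run from under 12 to 36 months.

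The size cannot be determined from the documents. It is nil if exits match across cohorts, or if all events fall in year 1 and no one exits before 12 months. Under the assumed exits at 12 to 15 months, expected episode ratios run from 1.08 to 1.50. With half of one cohort leaving at 12 months, subject-incidence ratios run from 1.02 to 1.48. The effect is larger for less common terms and for episode totals, and negligible for any TEAE if nearly every subject has one within a year. Chance variation in cohorts of 2 to 4 exceeds the shift.

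A reader might infer that these ratios estimate a bias in this trial, or that dose decisions are at risk. Neither follows. The ratios are illustrations. The analyses are descriptive with no hypothesis test, and the cohort reviews by the Safety Monitoring Committee require at least 4 weeks of data, so differences in year 2-3 follow-up do not drive escalation. Only interpretation of the final tables is affected.

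**What to change.** 1. **SAP 4.3.** State that only EOS assessments close to Month 36 (for example ±1 month by study day) enter the Month 36 row. Show earlier EOS values in a separate early-EOS or last-on-study row, with the study day.
2. **SAP 7.1.** Tabulate follow-up duration by cohort: n, median, range and total person-time.
3. **SAP 7.2.5.** Keep the crude tables. Add TEAE incidence and episodes by cohort over a common period (for example infusion to Week 52, with the number followed to Week 52), or episodes per person-year.

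The cost is one mapping rule and two small tables, using data already collected. The downsides are fewer or no subjects in some Month 36 rows, and that exits before Week 52 remain incomplete within the common period. Episodes per person-year avoid the second problem but average over a rate that may fall with time since infusion.
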